T2: Exit Survey

- Acceptability and implementation measures for the MyVoice tool
- Reproductive knowledge (ReproKnow)
- Self-efficacy (Perceived Efficacy in Patient-Provider Interactions [PEPPI])
- Decision Conflict Scale (Low Literacy version)
- Interpersonal Quality of Family Planning (IQFP) Scale

T3: Provider Survey

- Providers' experiences with the study as well as information related to encounters with patients enrolled in the study

T4: 3 Month Survey

- National Survey of Family Growth Family Planning Services Question
- Self-efficacy (Perceived Efficacy in Patient-Provider Interactions [PEPPI])
- Reproductive knowledge (ReproKnow)
- London Measure of Unintended Pregnancy

D. Risk/Benefit Assessment

Known Potential Risks

- Discomfort- Study activities involve information regarding reproductive health; some individuals may be uncomfortable discussing this topic.
- Invasion of Privacy- Participants may feel uncomfortable discussing their reproductive health where other individuals may hear them.
- Breach of Confidentiality- Any possibility that de-identified information could be viewed by unauthorized parties.

Known Potential Benefits

- This pilot study will inform the procedures and practices related to a future full-scale testing of a patient-facing decision support tool for family planning. Our study team and others have demonstrated that women with rheumatic diseases do not receive adequate family planning care. We will not directly counsel patients about their particular risks, and therefore, patients will not receive a direct benefit from their participation. However, they may learn more about their family planning options in the context of their diseases.

Assessment of Potential Risks and Benefits

- Discomfort- We will minimize occurrence of discomfort by being clear about the content of the study tool and assessment measures during recruitment. All questions in study surveys and interviews will be optional, and participants will be told they can skip any question they do not wish to answer.
- Invasion of Privacy- The study will not be discussed with potential or current participants in public settings. Conversations about the study will only occur in private exam rooms or research spaces or via email or phone conversations. We will minimize risk by placing phone calls while in a private room and asking the potential participant whether they are in a private location before discussing the study.

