For telemedicine participants, research coordinators will administer all surveys over the phone to participants and record their responses on a paper form. For clinic participants, research coordinators will allow participants to complete paper copies of the surveys themselves. Once REDCap is accessible again, the coordinator who administered the surveys will then record participant responses in REDCap manually and retain all paper copies.

If REDCap experiences issues while participants are logged in and completing surveys, the research coordinator will contact the REDCap support administrator at [Pitt Biomedical Informatics [contact]](mailto:[contact]) to attempt to restore any survey responses already recorded. If REDCap is still experiencing issues, the study will continue with paper form protocol as described above.

F4b. Internet Connection Issues

Should telemedicine participants experience an issue with their own internet connectivity/WiFi that prevents them from logging in to REDCap, the research coordinator will administer the surveys over the phone while logged in to REDCap and will enter all responses in real time.

For clinic participants, any issues with internet connectivity/WiFi within the clinics will follow paper form protocol by having participants complete the surveys on a paper copy of the surveys. Once access to an internet connection/WiFi is regained, the coordinator who administered the surveys will then record participant responses in REDCap manually and retain all paper copies.

I. Study Procedures

After eligible participants are screened and enrolled, participation in the study can begin. While it is preferred that participants answer as many questions on the surveys and complete as much of the study activities as they can, participants will be reminded that all questions and activities throughout the study are completely voluntary, and they do not need to answer any questions they do not wish to answer. In this case, there is a “prefer not to answer” response for all survey questions.

G1. Randomization

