Do you have any additional questions about the information we just reviewed together?

If any questions do arise, please don't hesitate to ask. I'll also give you my information at the end of the interview so you can follow up with me if you wish.

Do you have any questions for me at this point?

I will turn on the recorder now.

I. MyVoice:RD Feedback

- Please tell me your thoughts about MyVoice:RD.

[Prompt] What did you like about it? What did you dislike?

[Prompt] Did you learn anything about pregnancy, parenthood, or birth control related to women with rheumatic diseases from the decision aid?

[Prompt] Has MyVoice:RD been helpful to you? Did it help you to have a conversation with your rheumatologist related to your reproductive health? Did MyVoice:RD help you make decisions related to your reproductive goals (parenthood, pregnancy, or choice of contraception)? If yes, tell me about that.

[Prompt] What can we do to make the tool better?

- Is MyVoice:RD appropriate for women with rheumatic diseases? Is it valuable?
- How usable is MyVoice:RD?

[Prompt] What features were easy to use? What features were too complex?

[Prompt] Do you need help using MyVoice:RD?

[Prompt] Were the different parts of MyVoice:RD well-integrated?

- What are the barriers to using MyVoice:RD?

[Prompt] Did using MyVoice:RD require an excessive amount of time?

- What are the facilitators to using MyVoice:RD?

[Prompt] Did anything help you to use MyVoice:RD

- Are there any situations where you think MyVoice:RD would be particularly helpful?
Are there any situations or practices where you think MyVoice:RD would not be helpful?

II. Reproductive Health Discussions with your rheumatologist

- Did you discuss your reproductive goals or plans (including parenthood, pregnancy, or choice of birth control) with your rheumatologist during your last visit? If yes, how did that discussion go? If no, why not?

[Prompt] Who initiated the conversation? Who was in the room?

[Prompt] Did you feel heard? Did your provider help you understand your reproductive decisions?

[Prompt] Did your provider listen to the things that matter most to you about your reproductive decisions?

[Prompt] How much effort was made to include what matters most to you in choosing what to do next?

- Did MyVoice:RD influence your discussions with your rheumatologist? If yes, how?
- Did you have reproductive health discussions with your rheumatologist before you used MyVoice:RD?

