facilitate coding and thematic analysis. Transcripts were reviewed by two experienced qualitative analysts with master's degrees in public health and sociology, respectively ([name], [name]). [name] and [name] used an open coding approach to identify themes that arose inductively, and subsequently refined the codebook based on the most frequent and important codes. [name], a trained research assistant, also independently coded the transcripts. As a form of investigator triangulation, the analysts and P.I. ([name]) used a consensus approach to reconcile coding and create new codes. Focus coding was used to re-review all transcripts and synthesize themes.

RESULTS

Sample Characteristics

Fifty-five patients consented to participate in the study, among whom 46 patients were randomized to a study arm. Forty patients completed the study, among whom 31 patients were randomized to the MyVoice:Rheum intervention and 9 were randomized to the control arm. The most common rheumatic disease diagnoses were SLE, RA, and myositis. Most participants identified as heterosexual, and nearly half of all participants were married. More than half of participants had at least a college degree. Over 40% of participants identified their rheumatologist as their main health provider. Most participants had never been pregnant, and approximately 10% had a diagnosis of infertility. Over two-thirds of participants used a method of contraception.

Quantitative Outcomes

MyVoice:Rheum and the control pamphlet were both rated as feasible, acceptable, usable, and valuable by study participants. The minimum threshold score of 3.5 for the Acceptability of Intervention Measure (AIM) was met or exceeded by 96.8% of MyVoice:Rheum users and 88.9% of controls; average AIM scores for MyVoice:Rheum and controls were 4.4 (S.D. 0.58) and 3.97 (S.D. 0.65), respectively. The minimum threshold score of 3.5 for the Intervention Appropriateness Measure (IAM) was met or exceeded by 96.8% of MyVoice:Rheum users and 88.% of controls; average IAM scores among MyVoice:Rheum and controls were 4.48 (S.D. 0.60) and 4.11 (S.D. 0.85), respectively. System Usability Scale scores for MyVoice:Rheum users were rated in the range of "excellent", whereas scores for pamphlet users were rated in the range of "very good" (83.0 vs. 79.3, respectively).

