Approximately 55% of MyVoice:Rheum users vs. 44% of control participants discussed any family planning issues, plans, or questions with their rheumatologists during their clinic visit. Among these participants, 55% of MyVoice:Rheum users indicated that the tool influenced their decision to discuss family planning with their rheumatologists as compared to 44% of controls. Among MyVoice:Rheum users, self-efficacy scores on the PEPPI scale rose from a pre-test mean of 3.47 (S.D. 1.19) to a post-test mean 4.07 (S.D. 0.82) (mean difference: 0.59 (S.D. 0.91)).

Overall reproductive knowledge scores on ReproKnow rose from a pre-test mean of 5.77 (S.D. 1.76) to a post-test mean of 7.27 (S.D. 1.17) (mean difference: 1.50 (S.D. 1.93)). Reproductive knowledge appeared to increase across the ReproKnow domains of birth outcomes, fertility, contraception, pre-pregnancy planning, and pregnancy management.

Qualitative Outcomes. The following themes emerged from interviews with MyVoice:Rheum users: 1) MyVoice:Rheum was feasible, informative, usable, and customizable to the user; 2)

MyVoice:Rheum users felt prepared to initiate and engage in family planning conversations with their rheumatologists; 3) MyVoice:Rheum optimally should be provided for patients to review immediately prior to the rheumatology encounter, around the time of the initially RMD diagnosis and periodically afterwards; 4) Family planning conversations at the rheumatology visit were facilitated by respectful and trusting relationships with the rheumatologist, whereas distrustful relationships and rushed visits were a barrier to family planning conversations; 5) Suggested modifications to MyVoice:Rheum included tools directed towards clinicians to facilitate patient-centered care, and information modules for partners or family members. Representative quotations are presented in.

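### The 44% of controls said to have been influenced by their material cannot be a share of the controls who had a discussion

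*Combined protocol and SAP*

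**What the plan says.** Three statements in the Results part of section N (Statistical Analysis Plan) bear on this.

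- Sample Characteristics gives the completers by arm: "31 patients were randomized to the MyVoice:Rheum intervention and 9 were randomized to the control arm". It also gives 46 randomized in total, without a split by arm.
- Quantitative Outcomes gives the discussion rates: "Approximately 55% of MyVoice:Rheum users vs. 44% of control participants discussed any family planning issues, plans, or questions with their rheumatologists".
- The next sentence gives the influence result: "Among these participants, 55% of MyVoice:Rheum users indicated that the tool influenced their decision to discuss family planning". For controls, the same sentence puts the figure at 44%.

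Neither sentence gives a numerator or a denominator. The two pairs of percentages are identical.

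Two other places affect what the denominators could be. Answers were voluntary: section D (Risk/Benefit Assessment) says "All questions in study surveys and interviews will be optional", and section I (Study Procedures) tells participants that "they do not need to answer any questions they do not wish to answer". The Interview Guide in Appendix M, part II, has one item beginning "Did you discuss your reproductive goals or plans" and a separate item, "Did MyVoice:RD influence your discussions with your rheumatologist? If yes, how", with no skip instruction between them.

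**The concern.** The influence sentence follows directly on the discussion rates and concerns the decision to hold a discussion. A reader will therefore take its opening phrase to mean the women who had one. On that reading, 55% against 44% is the proportion of discussions credited to the material in each arm. With only 9 control completers, the subgroup of controls who had a discussion is too small to produce 44%.

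The discussion rates are what the Measures part of section N names as the preliminary assessment of effectiveness. The influence result stands beside them and appears to favour MyVoice. If the percentages were in fact computed on whole arms, the counts would be 17 and 4, the same as the counts of women who had a discussion. If, in addition, only women who had a discussion could report influence, the share among them would be 17/17 and 4/4, or 100% in both arms, with no difference between them. If the second pair was repeated from the first, the true result is not reported at all. The text does not let a reader tell these cases apart.

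**Working it through.** **Inputs**

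- Completers: 31 MyVoice, 9 control (Results, Sample Characteristics).
- Randomized: 46 in total (same place). The control arm therefore had at least 9 and at most 46 − 31 = 15 women.
- Discussed family planning: about 55% MyVoice, 44% control (Quantitative Outcomes).
- Said the material influenced the decision: 55% MyVoice, 44% control (next sentence).

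**Step 1. Confirm the working denominators.** The proportions meeting the acceptability threshold are printed as 96.8% and 88.9%. These are 30/31 = 96.8% and 8/9 = 88.9%, so the quantitative results use 31 and 9.

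**Step 2. Reproduce the discussion rates.** 17/31 = 54.8% and 4/9 = 44.4%. Both printed figures are recovered. For any control group of 1 to 15, 44% (rounded or truncated) occurs only as 4/9. So 4 controls had a discussion.

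**Step 3. Try to obtain 44% among the controls who had a discussion.** For each possible number of respondents m, the attainable value j/m closest to 44% is:

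| m | closest to 44% |
|---|---|
| 1 | 0/1 = 0% |
| 2 | 1/2 = 50% |
| 3 | 1/3 = 33.3% |
| 4 | 2/4 = 50% |
| 5 | 2/5 = 40% |
| 6 | 3/6 = 50% |
| 7 | 3/7 = 42.9% |
| 8 | 4/8 = 50% |
| 9 | 4/9 = 44.4% |

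Only m = 1 to 4 is available, and nothing there gives 44%. The closest value is 50%, 6 points away. With 4 respondents, one woman moves the result by 1/4 = 25 points. The smallest m that works is 9, which would require all 9 completers to have had a discussion, contrary to the preceding sentence. The next is 16 (7/16 = 43.75%), above the largest possible control arm.

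**Step 4. Try to rescue the figure.**

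- *Unanswered items.* These only reduce m, and no m from 1 to 8 gives 44%.
- *The word 'approximately'.* It stands before the discussion rates. Suppose it allows anything from 40 to 48%. With up to 9 controls the options are 2/5, 3/7 and 4/9, still at most 4 discussions. With up to 15 controls the largest count is 7 (7/15 = 46.7%), still below the 9 needed.
- *Randomized women instead of completers.* The arm cannot exceed 15, so the previous limit of 7 applies.

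**Step 5. The MyVoice figure.** If all 31 completers answered both items, 17 had a discussion, and the closest values are 9/17 = 52.9% and 10/17 = 58.8%, so 55% cannot occur. With unanswered items it can. By rounding, with n ≤ 31, 55% arises as 6/11, 11/20, 12/22, 16/29 or 17/31. For example, 11/20 could have had a discussion and then 6/11 reported influence, or 11 of the 17 could have answered the second item and 6 said yes. Truncation would add 5/9, 10/18 and 15/27. This arm is suggestive only, and the conclusion does not rest on it.

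**Step 6. Whole-arm denominators.** 17/31 = 54.8% and 4/9 = 44.4% match both printed influence figures.

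**The case against.** The strongest reply is grammatical. The subjects of the preceding sentence are the users in one arm and the participants in the other, so the opening phrase could refer to all completers. On that reading 17/31 and 4/9 fit and no number is wrong. This stands as a possibility: what is established is a mismatch between the figure and the group it is said to describe, not which of the two is at fault. It is the less natural reading, however. It also makes the influence counts equal the discussion counts in both arms, and the sentence would still need rewording.

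The Interview Guide is limited help in deciding. It asks about influence separately, which is compatible with a whole-arm denominator. But its wording presupposes that discussions took place, it asks about influence on the discussions and not on the decision to have one, and it names only MyVoice. The exit-survey items are not in the available text. I therefore do not rely on it.

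Nor are a repeated pair and a whole-arm calculation the only possible causes; another typing error in either sentence could produce the same mismatch.

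Finally, the result carries little weight. The Measures part of section N says that pilot studies are not built to test hypotheses and does not list the influence item. That is right, and it is why the point is rated minor.

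**Conclusion.** The concern holds. Taken as a share of the controls who had a discussion, 44% is arithmetically impossible: at most 4 women qualify and at least 9 are needed. This rests on the 9 control completers, on the printed 44% discussion rate and on the natural reading of the sentence. It survives rounding or truncation, unanswered items, a loose reading of the discussion rate and any control arm of up to 15. The MyVoice figure of 55% is impossible only if all 31 completers answered both items, which the documents do not establish.

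Whether the percentages or the description of the group is wrong cannot be decided from the text. The consequence is confined to one descriptive sentence. Until it is corrected, 55% against 44% should not be read as the share of discussions credited to the material.

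**What to change.** Recount from the study data. For each arm, report n/N for having had a discussion and n/N for the material having influenced the decision, with N the number who answered that item. Then correct whichever is wrong:

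- If the denominators were the women who had a discussion, replace the percentages.
- If the denominators were whole arms, replace the opening phrase, state the denominator, and do not present 55% against 44% as the share of discussions attributed to the material.

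With so few controls in the subgroup, counts should accompany any percentage. The cost is one cross-tabulation and one rewritten sentence.

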Participants are able to withdraw from study participation at any time for any reason. To withdraw, a participant must either provide verbal or written notification that they want to withdraw from the study and discontinue any ongoing study activities. Any information and data collected prior to withdrawal will be retained and can be used for research-related purposes, unless specified by participant at withdrawal.

At the time of participant withdrawal, research coordinators will load a Vincent card for the withdrawn participant with the appropriate payment amount as delineated in the Payment Protocol section. Coordinators will then complete the Withdrawal Form in REDCap.

J2. Lost to Follow Up

Participants will be deemed lost to follow up if they participate in the intervention but are unable to be reached for future study activities (time point T2). To clarify, if participants do not complete the exit survey/interview after their rheumatology appointment, research coordinators will attempt to schedule study activities 24-48 hours after their visits (described in Study Procedures section). If study staff is unable to reach them to schedule and they do not hear from the participant to complete the study activities, participants will then be considered lost to follow up. Coordinators will then complete a Lost to Follow Up form in REDCap.

Note: Because T4 study activities are supplemental to the main study data, participants that cannot be reached to complete the final 3-month survey will not be considered lost to follow up.

K. SAFETY ASSESSMENTS

1. Study oversight is being conducted by an internally-appointed Safety Officer, [name], Assistant Professor in the Department of Obstetrics, Gynecology & Reproductive Sciences at the University of Pittsburgh.

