While pilot studies are not designed to test hypotheses, we preliminarily assessed the effectiveness of MyVoice:Rheum in prompting family planning discussions by comparing the incidence in which these discussions occurred across the study arms. We also evaluated self-efficacy and knowledge scores within each arm before and after the intervention. Self-reported efficacy in communicating with providers was assessed using a modified version of the validated five-item Perceived Efficacy in Patient-Provider Interactions (PEPPI) scale. Rheumatology-specific reproductive health knowledge was assessed via ReproKnow, a measure developed and preliminarily validated by our team that covers domains of contraception safety and efficacy, pregnancy management, pre-conception planning, medication safety, fertility; a score of nine indicates the highest level of reproductive knowledge. Overall knowledge scores as well as scores related to specific domains of reproductive knowledge were calculated across individuals in each study arm. Among MyVoice:Rheum users only, knowledge was assessed again three months after the intervention.

Analysis

Quantitative. Quantitative measures of demographics, feasibility, and acceptability were assessed via descriptive statistics. Among MyVoice:Rheum users and controls, we conducted paired comparisons pre- and post-intervention regarding self-efficacy and reproductive health knowledge, using McNemar's test for proportions and Wilcoxon's signed rank test for means. Calculations were performed using Stata 17.0.

Qualitative. A deductive approach was used to prepare the preliminary codebook, which was organized by the following domains: feasibility and acceptability; family planning discussed at rheumatology visit (yes/no), and reasons why or why not; barriers and facilitators to discussing family planning at the rheumatology visit; ideal timepoints and contexts to use the tool; and suggested modifications. Interview transcripts were entered into NVivo software to

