Three-month outcomes. Most MyVoice:Rheum users engaged in interviews three months following the intervention (N=30). Some MyVoice:Rheum users indicated receipt of family planning services after the intervention, including: 1) initiation of a new birth control method (N=7); 2) counseling about birth control or pregnancy planning from a clinician (N=4); and/or 3) a clinic visit or medical test related to birth control or pregnancy planning (N=3). When reproductive knowledge was re-evaluated again three months, overall scores remained significantly higher than pre-intervention scores (pre-intervention mean 5.77 (SD 1.76) vs. post-intervention 7.27 (1.17), mean difference 1.50 (1.93)).

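### The immediate and three-month ReproKnow results are identical in every figure, so at least one appears misreported and knowledge retention at three months cannot be verified

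*Combined protocol and SAP*

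**What the plan says.** Section C lists ReproKnow in three patient surveys: T0 (baseline), T2 (exit) and T4 (three months). Sections G2d and G3d place T2 no later than 48 hours after the intervention. Section N, Measures, confirms that the three-month measurement was a further assessment: "Among MyVoice:Rheum users only, knowledge was assessed again three months after the intervention". Section N, Analysis, says "we conducted paired comparisons pre- and post-intervention regarding self-efficacy and reproductive health knowledge", with Wilcoxon's signed rank test for means.

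Section N, Results, then gives two knowledge results:

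- Quantitative Outcomes (immediate): scores "rose from a pre-test mean of 5.77 (S.D. 1.76) to a post-test mean of 7.27 (S.D. 1.17) (mean difference: 1.50 (S.D. 1.93".
- Three-month outcomes: "overall scores remained significantly higher than pre-intervention scores (pre-intervention mean 5.77 (SD 1.76) vs. post-intervention 7.27 (1.17), mean difference 1.50 (1.93".

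On numbers, 40 women completed the study, "among whom 31 patients were randomized to the MyVoice:Rheum intervention". At three months, most MyVoice users "engaged in interviews three months following the intervention (N=30". Neither knowledge result comes with a paired n, a p-value, a confidence interval or the outcome of the signed rank test. The top ReproKnow score is nine; the document does not say whether scores are whole numbers.

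**The concern.** Two assessments of the same women about three months apart should give two sets of summary figures. Here the two sets agree in all six numbers, so the implied mean change from T2 to T4 is 7.27 − 7.27 = 0.00, with no change in spread either. The likeliest explanation is that one set was copied into the place of the other.

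The three-month sentence is the document's only statement that the knowledge gain lasted, and it claims statistical significance. The same figures are also its only numerical result for immediate knowledge. If one set is a copy, one of the two time points has no reported result. Section L commits the sponsor to submitting results to ClinicalTrials.gov and seeking publication, and the pilot is meant to inform a larger trial, so an unsupported statement on durability could travel further.

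**Working it through.** **1. Which figures ought to differ.**

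| Figure | Immediate | Three-month | Explained by a shared baseline or by subtraction? |
|---|---|---|---|
| Baseline mean | 5.77 | 5.77 | Yes, if the same women are in both comparisons |
| Baseline SD | 1.76 | 1.76 | Yes, on the same condition |
| Follow-up mean | 7.27 | 7.27 | No |
| Follow-up SD | 1.17 | 1.17 | No |
| Mean difference | 1.50 | 1.50 | Yes: 7.27 − 5.77 = 1.50 |
| SD of difference | 1.93 | 1.93 | No |

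The case rests on the three rows marked No.

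**2. Internal consistency of the block.** The correlation between baseline and follow-up implied by the three SDs is (1.76² + 1.17² − 1.93²) / (2 × 1.76 × 1.17) = (3.0976 + 1.3689 − 3.7249) / 4.1184 = 0.7416 / 4.1184 = 0.18, or 0.17 to 0.19 allowing for rounding. The block is possible as a set of figures. The problem is only that it appears twice.

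**3. Chance of a match.** Studies of 30 women were simulated with whole-number scores from 0 to 9 and one shared baseline. T2 and T4 both had mean 7.27, SD 1.17 and correlation 0.18 with baseline, so there was no true change between them. There were 400,000 studies per setting. The three free figures all matched to two decimals as follows:

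| Assumed T2–T4 correlation | Matches | Share |
|---|---|---|
| 0.3 | 39 | 0.010% |
| 0.5 | 67 | 0.017% |
| 0.7 | 122 | 0.031% |
| 0.9 | 371 | 0.093% |

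That is about 1 in 10,000 to 1 in 1,100. A true change in the mean between T2 and T4 would make a match rarer still.

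**4. What sample size fits.** Assume whole-number scores and take n from 15 to 31, the upper limit being the number of MyVoice completers. The three means can be reached together only at n = 22, 26 and 30. Adding the SDs leaves only n = 30:

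- Baseline: sum 173, sum of squares 1087. Mean 173/30 = 5.77; SD √[(1087 − 173²/30)/29] = 1.76.
- Follow-up: sum 218, sum of squares 1624. Mean 218/30 = 7.27; SD √[(1624 − 218²/30)/29] = 1.17.
- Difference: sum 45, sum of squares 175. Mean 45/30 = 1.50; SD √[(175 − 45²/30)/29] = 1.93.

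n = 31 fails, since 225/31 = 7.26 and 226/31 = 7.29. This does not identify the source of the block. Thirty pairs would suit T4, where 30 women were interviewed. They would equally suit T2 with one of 31 pairs missing, because Section I says "all questions and activities throughout the study are completely voluntary".

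**5. What the printed block would show at n = 30.** Standard error 1.93/√30 = 0.352; t = 1.50/0.352 = 4.26 on 29 degrees of freedom, p = 0.0002; 95% CI 0.78 to 2.22. The paired t stands in for the signed rank test, which needs individual scores.

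**The case against.** The strongest reply is that neither block is numerically wrong. The three-month sentence calls its second value post-intervention, not three-month. It may correctly restate the exit-survey result and simply omit the T4 figure. On that reading the immediate paragraph, which is clearly labelled pre-test and post-test and has nothing odd within it, stands as printed. This is possible. But the sentence presents the block as the three-month evidence, so on this reading too a claim about three months rests on other data and no T4 score is given. The correction is the same.

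Some narrower points stand:

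- The count of 30 is of interviews. Sections G2f and G3f arrange the T4 interview separately from the T4 survey that carries ReproKnow, and no T4 survey count is given. This further weakens any link between n = 30 and T4.
- The immediate paragraph also says in words that knowledge appeared to rise in five domains, so the duplicated block is the only numerical immediate result, not the only mention.
- The Analysis text names the signed rank test for pre/post comparisons and does not expressly assign it to T0–T4.
- The simulation gives the chance of a match if both reports are right, under stated assumptions. It is not the probability of an error.

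It can also be said that this is a reporting matter outside the main outcomes. Section J2 reasons that "Because T4 study activities are supplemental to the main study data", and Section F makes feasibility and acceptability the main outcomes. That limits how much depends on the error. It does not supply the missing result.

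**Conclusion.** The concern holds and should be fixed. The two results agree in all six figures, and three of those have no ordinary reason to agree. At least one block appears misreported, the document does not show which, and the statement that knowledge was still significantly higher at three months cannot be verified. The immediate result is in question only to the extent that it may be the misplaced one.

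The printed gain of 1.50 (95% CI 0.78 to 2.22 at n = 30) is clear evidence of improvement for whichever time point it belongs to. The gain at the other time point is unknown, and no corrected value can be derived from the document. The chance-match figures assume whole-number scores, 30 pairs, no true change from T2 to T4 and a T2–T4 correlation of 0.3 to 0.9; the interval assumes n = 30. The side-by-side comparison needs none of these. The pilot's feasibility and acceptability conclusions are not affected.

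**What to change.** Recompute the T0–T2 and T0–T4 paired summaries from the REDCap data. For each, report:

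- the paired n, and the baseline mean and SD in that paired set;
- the follow-up mean and SD;
- the mean difference with its SD and 95% CI;
- the signed rank result, stating for T0–T4 that the same test is being applied.

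State whether ReproKnow is scored in whole numbers. Correct whichever block is wrong, and label the T4 value as three-month. Keep the statement on three-month knowledge only if the T4 scores support it; otherwise amend or withdraw it.

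The cost is one re-run of an existing summary and a text correction, with no new data collection. The durability statement may become less favourable, or the immediate gain may change if that paragraph holds the wrong block.
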